Protocol Summary

This document represents the protocol summary for the study on human subjects. The study will be carried out in accordance with ICH GCP, National Standard of the Russian Federation GOST 52379-2005 "Good Clinical Practice", Helsinki Declaration of World Medical Association, relevant requirements of the regulatory authorities as well as the study procedures.

Title of Study

Multicenter double-blind placebo-controlled parallel-group randomized clinical study of efficacy and safety of Tenoten for children liquid dosage form therapy in infants with sequelae of perinatal brain injury.

Phase: III

Sponsor: OOO "NPF "Materia Medica Holding", Moscow, Russia

Protocol No. MMH-TD-004

Study purposes

- To assess the clinical efficacy of Tenoten for children liquid dosage form therapy (10 oral drops per day for 12 weeks) in infants with sequelae of perinatal brain injury (mild-to-moderate cerebral hypoxia-ischemia and/or mild-to-moderate intracranial hemorrhage).
- To assess the safety of Tenoten for children liquid dosage form therapy (10 oral drops per day for 12 weeks) in infants with sequelae of perinatal brain injury (mild-to-moderate cerebral hypoxia-ischemia and/or mild-to-moderate intracranial hemorrhage).

Endpoints

Primary endpoint

1. Percentage of patients with a 4 and more point increase of the total score according to Jurba-Mastyukova psychomotor development scale by the end of the treatment course compared to baseline.

Secondary endpoints

1. Percentage of patients with normal psychomotor development (≥ 27 scores on Jurba-Mastyukova scale) by the end of the treatment course compared to baseline.
2. Mean Cognitive adaptive test/Clinical linguistic and auditory milestone scale (CAT/CLAMS) by the end of the treatment course compared to baseline.

3. Percentage of patients with normal psychomotor development (CATS/CLAMS + Gross motor developmental quotients score ≥ 75) by the end of the treatment course compared to baseline.
4. Clinical Global Impression scale - Efficacy Index (CGI-EI) score by the end of the treatment course.

Safety assessment

- Adverse events during the treatment, their severity, treatment relatedness, and outcomes.

Study design

Study design: multicenter, double-blind, placebo-controlled, parallel-group, randomized clinical study to assess efficacy and safety of the study therapy.

The study will enroll children of both genders aged from 29 days (end of neonatal period) up to 9 months on outpatient neurologist's observation due to sequelae of perinatal brain injury (mild-to-moderate cerebral hypoxia-ischemia and/or mild-to-moderate intracranial hemorrhage). The subjects of the study are not to be scheduled for any other treatments besides the investigated therapy within 12 weeks of the trial.

After parent/adoptive parent has signed the patient information sheet (informed consent form) the subject's medical history will be collected, physical examination will be performed, body weight, length, and head circumference will be measured. The infant neurological status will be assessed including psychomotor development according to Jurba-Mastyukova scale and Clinical Adaptive Test/Clinical Linguistic and Auditory Milestone (CAT/CLAMS) scale. Concomitant therapy will be recorded. If the subject meets inclusion criteria and has no exclusion criteria he/she will be included in the study and randomized at Visit 1 into one of the two groups: group 1 will receive Tenoten for children (oral drops) 10 oral drops per day for 12 weeks; group 2 - Placebo 10 oral drops per day for 12 weeks.

The subject will be observed for 12 weeks during which he/she will be examined by neurologist every 4 weeks (Visits 2, 3 and 4) in order to evaluate changes in physical and neuropsychological development, changes in neurological status, and to record potential adverse events, study treatment compliance.

At the final visit (Visit 4, Week 12) the neurologist will evaluate motor and mental development, fill in Jurba-Mastyukova and CAT/CLAMS scales, record adverse events, and assess the therapy compliance. Then the Clinical Global Impression – Efficacy Index (CGI-EI) scale will be filled in.

Music therapy, herbal baths, gymnastics and tactile stimulation based on the child's age are allowed during the study.

If the prohibited medicines are required for patients they will be withdrawn from the study and it will be considered as the absence of efficacy.

Inclusion and exclusion criteria

Inclusion criteria

1. Full-term infants aged 29 days to 9 months¹.
2. Diagnosis of sequelae of perinatal brain injury (mild-to-moderate cerebral hypoxia-ischemia and/or mild-to-moderate intracranial hemorrhage).
3. Jurba-Mastyukova total score < 27 and > 12.
4. Physical development parameters within 25-27 centiles.
5. Neurologist's outpatient observation.
6. Information sheet (informed consent form) for parents/adoptive parents for participation in the clinical study signed by the child's parents/adoptive parents.

Exclusion criteria

1. Previously diagnosed lesions, diseases and conditions:
 - 1.1. Cerebral ischemia (grade III).
 - 1.2. Intraventricular hemorrhage (grade III).
 - 1.3. Metabolic and toxic disorders affecting central nervous system (persistent neonatal hypoglycemia, hyperbilirubinemia associated with elevated indirect bilirubin, and other severe conditions).
 - 1.4. Intracranial birth injury, focal impairments due to brain injuries (pareses and paralyses).
 - 1.5. Sequelae of birth injury to spinal cord, cranial nerves and peripheral nervous system (peripheral pareses and paralyses).
 - 1.6. Different types of hydrocephalus.
 - 1.7. Symptomatic epilepsy and epileptic syndromes.
 - 1.8. Sequelae of perinatal central nervous system (CNS) infectious diseases (injury to CNS caused by neonatal sepsis, encephalitis, meningitis, meningoencephalitis, ventriculitis).
 - 1.9. Infectious diseases including congenital diseases (cytomegalovirus infection, rubella, herpesvirus or enterovirus infection, toxoplasmosis, syphilis, HIV infection, etc.).

¹ Full-term neonates, i.e. born at gestation term of 38-42 weeks with birth weight > 2500 g.

- 1.10. Chronic respiratory diseases originating in the perinatal period, including bronchopulmonary dysplasia.
- 1.11. Hereditary metabolic diseases including glycogen storage disease (glycogenoses, E74.0), galactose metabolism disorders (galactosemia, E74.2), other carbohydrate metabolism disorders (E74), glucosaminoglycan metabolism disorders (mucopolysaccharidoses, E76), aromatic amino-acid metabolism disorders (phenylketonuria, tyrosinemia, etc, E70), branched-chain amino-acid and fatty-acid metabolism disorders (maple-syrup-urine disease, E71), mitochondrial myopathy (G71.3).
- 1.12. Neurodegenerative diseases including Huntington disease (G10), copper metabolism disorder (Wilson disease, E83.0).
- 1.13. Chromosomal abnormalities.
- 1.14. Congenital anomalies [malformations] and deformities including congenital anomalies of nervous system and malformations of internal organs.
- 1.15. Congenital endocrine diseases (congenital hypothyroidism, hypoparathyroidism, adrenocortical dysfunction).
- 1.16. Malignant neoplasm / suspected malignant neoplasm.

2. Acute infectious disease, exacerbation / decompensation of diseases that may prevent the patients' participation in the clinical study.
3. Allergy/intolerance of any of the study treatment medications components.
4. Drug addiction, alcohol use in the volume over 2 alcohol units/day by the subject's parent(s)/adoptive parent(s).
5. Mental disorders of the patient's parent(s)/adoptive parent(s).
6. Participation in other clinical studies for a period prior to and during the course of this trial.
7. Other conditions complicating the subject's participation in the study (cannot make regular medical visits, moving, etc.).
8. Subjects whose parent(s)/adoptive parent(s), from the investigator's point of view, will not follow the study requirements or comply with the dosing regimen.
9. Patients whose parent(s)/adoptive parent(s) are related research staff of the clinical investigative site who are directly involved in the study or is a close relative of the investigator. Close relatives include spouse, parents, children or brothers (sisters) regardless of whether they are biological or adoptive ones.
10. Patients whose parent(s)/adoptive parent(s) is working in OOO "NPF "Materia Medica Holding", i.e. is the company official, temporary contract worker or an appointed official responsible for the study or their close relatives.

Discontinuation criteria

1. Inability or refusal of parent(s)/adoptive parent(s) to compliance the protocol.
2. Necessity in the products not allowed within the study.
3. Development of an adverse event requiring the product discontinuation.
4. Parents'/adoptive parents' wish to terminate the study early due to lack of therapeutic efficacy or for any other reason.
5. Cases not specified by the protocol when, according to the investigator, further subject's participation is dangerous.
6. Enrollment of an ineligible subject.

Number of subjects

Signing informed consent by the parent(s)/adoptive parent(s) of 184 patients is planned; this is supposed to assure completion of all protocol procedures by at least 144 subjects.

Treatment

Group 1

Name: Tenoten for children

Active ingredient (per 1.0 mL): affinity purified antibodies to brain-specific S-100 protein - 0.006 g*

* administered as a mixture of three active water dilutions of the substance diluted respectively 100¹², 100³⁰, 100⁵⁰ times

Excipients: Maltitol – 0.06 g; glycerol – 0.03 g; potassium sorbate – 0.00165 g; citric acid anhydrous – 0.0002 g; purified water – up to 1.0 mL

Dosage: Per os. 10 drops (0.5 mL) once daily 15 min prior to morning feeding approximately at the same time. Prior to administration the drops may be diluted in small amount (1-5 mL) of boiled water of room temperature

Dosage form: Oral drops

Description: Colourless or almost colourless clear fluid

Storage conditions: Store protected from light at temperature below 25°C. Keep out of the reach of children. Do not freeze

Group 2

Name: Placebo

Active ingredient (per 1.0 mL): NA

Excipients: Maltitol – 0.06 g; glycerol – 0.03 g; potassium sorbate – 0.00165 g; citric acid anhydrous – 0.0002 g; purified water – up to 1.0 mL

Dosage: Placebo using Tenoten for children scheme.

Dosage form: Oral drops

Description: Colourless or almost colourless clear fluid

Storage conditions: Store protected from light at temperature below 25°C. Keep out of the reach of children. Do not freeze

Treatment period

Tenoten for children/Placebo treatment period is 12 weeks.

Basic therapy

[figure not shown]
All subjects participating in the study will receive non-drug therapy in home conditions: music therapy, herbal baths, gymnastics and tactile stimulation based on the child's age.

Prohibited concomitant therapy

The following products (ATC group is specified in brackets) are not allowed 15 days prior to enrollment and throughout the study:

1. Psycholeptics (ATC group N05) including anxiolytics (tranquilizers), hypnotics and sedative products.
2. Psychoanaleptics (ATC group N06) including psychostimulants and nootropic agents:
 - pyrrolidine derivatives (racemates) – piracetam, etiracetam, aniracetam, etc.;
 - pyridoxine derivatives - pyritinol, biotredin;
 - GABA derivatives and analogues – gamma-aminobutyric acid, nicotinoyl gamma-aminobutyric acid, gamma-amino-beta-phenylbutyric acid hydrochloride, hopantemic acid, calcium gamma-hydrobutyrate;
 - ginkgo biloba;
 - neuropeptides and their analogues - methionyl-glutamyl-histidyl-phenylalanyl-prolyl-glycyl-proline;
 - amino acids and substances affecting excitatory amino acid system - glycine, pyridoxine + threonine;
 - polypeptides and organic composites - live stock cerebral cortical polypeptides, cerebrolysin;
 - substances from other pharmacological groups with nootropic effect (general tonic agents and adaptogens - acetylasparaginic acid, melatonin, lecithin, etc.).
3. Antiepileptic drugs (ATC group N03A).
4. Anticholinergic drugs (ATC group N04A).
5. Dopaminergic drugs (ATC group N04B).
6. Muscle relaxants (ATC group M03).
7. Antihypoxants and antioxidants (ethylmethylhydroxypyridine succinate, citicoline, etc.).
8. Agents improving metabolism and energy supply to tissues reducing tissue hypoxia (cytoflavin, corylip, eltacin, inosine, etc.).
9. Homeopathic products.
10. Vitamins and vitamin-like agents (ATC groups A11E, A11D, A11HA) – thiamine (vitamin B₁), pyridoxine (vitamin B₆), pyridoxal phosphate, nicotinic acid (vitamin PP), pantothenic (vitamin B₅) and pangamic (vitamin B₁₅) acids.
11. Products previously causing allergic reactions in the subjects.

Study design scheme

Schedule of study procedures

Procedure/visit	Visit 1 (Screening, Day 0)	Visit 2 (Week 4±5 days)	Visit 3 (Week 8±5 days)	Visit 4 (Week 12±5 days)
Signing patient information sheet	+			
Collection of complaints	+	+	+	+
Collection of medical history	+			
Objective examination	+	+	+	+
Neurological status	+	+	+	+
Body weight measurement	+			+
Body length measurement	+			+
Head circumference measurement	+			+
Evaluation of physical development by centile tables	+			+
Evaluation of psychomotor development using Jurba-Mastyukova scale	+	+	+	+
Evaluation of psychomotor development using CAT/CLAMS scale	+	+	+	+
Recording concomitant therapy	+	+	+	+
Evaluation of compliance with inclusion/exclusion criteria	+			
Randomization and prescription of the study therapy	+			
Drug issue	+	+	+	
Accounting and return of the product, determination of compliance		+	+	+
CGI score				+
Therapeutic safety evaluation		+	+	+

Statistical Analyses

The following rules and assumptions were taking into account when calculating the sample size: power of statistical criteria is equal to 80% (probability of non-missing the effect is equal to 0.8); probability of error of the first kind is $< 5\%$ (probability of erroneous decision on the effect presence < 0.05). The statistical criteria used are two-sided, sample size is based on the assumption of the expected effects according to the primary outcome measure claimed in the protocol.

It is supposed that the difference between proportions of subjects with increased Jurba-Mastyukova total score ≥ 4 scores by the end of the treatment course in Tenoten for children group compared to equivalent proportion of subjects in Placebo group is no less than 22% in favour of Tenoten for children.

Given the statistical terms mentioned above, the size of each group will be 72 subjects (PP analysis, total = 144).

Supposing potential withdrawal of at least 22% subjects at screening and during the study for various reasons, at least 92 subjects in each group (184 in total) will be required to be recruited with their parents/adoptive parents signing informed consent form.

Safety and tolerability analysis of the study therapy will be based on the data from all randomized subjects who have received at least one dose of the study product/placebo. Efficacy analysis will be based on the two samples - FAS (Full Analysis Set) and PP (Per Protocol set): ITT-analysis and PP-analysis, respectively.

SAS-9.4 software will be used for statistical analysis including various parametric and nonparametric tests.

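### CGI-EI (secondary endpoint 4) is scheduled only at Visit 4, with no rating at withdrawal, so by default its FAS analysis reduces to infants who attend that visit

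*Combined protocol and SAP*

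**What the plan says.** The fourth secondary endpoint is defined as "Clinical Global Impression scale - Efficacy Index (CGI-EI) score by the end of the treatment course". The Study design section ties the rating to the last visit: "At the final visit (Visit 4, Week 12) the neurologist will evaluate motor and mental development", and, after the other assessments at that visit, "Then the Clinical Global Impression – Efficacy Index (CGI-EI) scale will be filled in". In the Schedule of study procedures the CGI row carries one mark, under Visit 4. The schedule has no early-termination column, and nothing elsewhere asks for a rating when an infant leaves.

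The other efficacy scales are treated differently. The row "Evaluation of psychomotor development using Jurba-Mastyukova scale" is marked at Visits 1 to 4, and so is the CAT/CLAMS row.

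On withdrawals, the Study design section has one outcome rule: "If the prohibited medicines are required for patients they will be withdrawn from the study and it will be considered as the absence of efficacy". The Discontinuation criteria also list, as item 3, "Development of an adverse event requiring the product discontinuation" and, as item 4, a parental wish to stop, with lack of therapeutic effect named as one possible reason. The Statistical Analyses section plans efficacy analyses on FAS and PP sets without defining either, and gives no missing-data rule for any endpoint.

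**The concern.** Some of the routes out of the study are linked to how the infant is doing: need for a prohibited product, an adverse event that stops treatment, or perceived lack of effect. These are infants whose rating on a global efficacy index matters most. Under the schedule as written they have none, unless they happen to reach Visit 4.

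For Jurba-Mastyukova and CAT/CLAMS, an infant who leaves after Week 4 or Week 8 still has a post-baseline value that an analysis could use. CGI-EI has nothing earlier to draw on. At stake is whether the FAS result for endpoint 4 describes the randomised groups or only those who stayed for 12 weeks. If it is the latter, endpoint 4 could disagree with the primary endpoint simply because it is computed on different infants.

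**Working it through.** **Inputs.** 184 infants with signed consent and at least 144 completing (Number of subjects); 72 per group for PP and 92 per group recruited (Statistical Analyses); loss described as "Supposing potential withdrawal of at least 22% subjects at screening and during the study for various reasons".

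**The plan's own figure.** N/(1 − d): 72/0.78 = 92.3 per group and 144/0.78 = 184.6 in total. The stated 92 and 184 are these values rounded down. Planned losses are 184 − 144 = 40, and 40/184 = 21.7%.

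**Share of randomised infants without CGI-EI.** The 22% pools screening losses with losses during the study. A screening failure is never randomised and needs no rating. If s of the 40 are lost at screening, the share of randomised infants missing Visit 4 is (40 − s)/(184 − s):

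| s | Missing / randomised | Share |
|---|---|---|
| 0 | 40/184 | 21.7% |
| 10 | 30/174 | 17.2% |
| 20 | 20/164 | 12.2% |
| 30 | 10/154 | 6.5% |
| 40 | 0/144 | 0% |

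The split is not stated, so the whole range is open. The plan says at least 22%, so 21.7% is the top of the range under the planned numbers, not a ceiling on what may happen.

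**Possible effect on the comparison (assumed figures only).** Endpoint 4 is a score; a favourable/unfavourable split is used here only to show the mechanism. Take s = 20, so 82 are randomised per arm, and suppose 41 (50%) are truly favourable in each arm.

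- Leavers have the same favourable rate as those who stay: both arms still read 50%, with no bias.
- All leavers unfavourable, 10 lost per arm: 41/72 = 56.9% in both arms. The level is 6.9 points too high and the difference is still zero.
- All leavers unfavourable, 13 v 7 lost: 41/69 − 41/75 = 59.4% − 54.7% = 4.8 points, favouring the arm that lost more. SE = √(0.594 × 0.406/69 + 0.547 × 0.453/75) = 8.2 points.

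At the extreme of no screening loss (92 per arm), with all leavers unfavourable:

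- 46 favourable per arm, 25 v 15 lost: 46/67 − 46/77 = 68.7% − 59.7% = 8.9 points (SE 8.0), where the true difference is zero.
- True rates 50/92 v 40/92 (10.9 points), 15 v 25 lost: 50/77 − 40/67 = 64.9% − 59.7% = 5.2 points, so a real difference is roughly halved.

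The bias can therefore be nil, can create a difference, or can hide one.

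**The case against.** The strongest reply is that the documents never restrict CGI-EI to completers. They plan an FAS analysis of efficacy, and the absence-of-efficacy rule names no endpoint, so it could be read as giving a CGI-EI entry too. The text calls itself a protocol summary, and silence in it is not a completers-only rule. This stands against two stronger readings that a reader might infer: that early leavers can never be scored, and that the plan prescribes a completers-only comparison. Neither is written. A value could be assigned by rule without any rating, so an FAS analysis is undefined rather than impossible. Nor is there support for reading the absence-of-efficacy rule as limited to the yes/no endpoints.

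The reply does not remove the gap. The rule covers prohibited-medicine cases only and does not say what CGI-EI value results. Withdrawals for an adverse event or for lack of effect have no rule at all. Naming an FAS does not produce a rating that was never made.

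A second reply is that the missing-data gap is general: Week 4 and Week 8 values on the other scales help only if some rule uses them, and none is stated. That is fair. What is particular to CGI-EI is that no interim rating exists for any rule to use.

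A third is that leavers are not all failures. Refusal, ineligible enrolment and unrelated parental reasons are also listed. This stands too, and it is why the documents do not support saying that the index is overstated in both arms as a matter of fact. The spurious differences illustrated are also only about 0.6 and 1.1 standard errors (4.8/8.2 and 8.9/8.0).

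**Conclusion.** The concern holds as a gap in data collection. Text and schedule agree that CGI-EI is rated once, at Visit 4, with no interim or exit rating. Infants withdrawn earlier, some for reasons linked to outcome, have no observation, so the FAS analysis of endpoint 4 falls back by default on those who attend Visit 4.

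Under the planned numbers, between 0 and 21.7% of randomised infants are affected, or 12.2% if half of the losses occur at screening. The documents give neither the loss by arm nor the leavers' outcomes, so no bias of a given size or direction can be claimed; the illustrations rest on an assumed dichotomy, assumed rates and, where bias appears, every leaver being unfavourable.

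This is one of four secondary endpoints. The primary endpoint is rated at every visit, and the figures of 72, 144 and 184 rest on the primary endpoint, so neither changes. It is worth correcting before enrolment because a missed exit rating cannot be recovered afterwards.

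**What to change.** - In the CGI row of the schedule, add that CGI-EI is completed at the last contact of any randomised infant withdrawn before Visit 4. Use that rating as the end-of-treatment value in the FAS.
- State how absence of efficacy is entered on CGI-EI for prohibited-medicine withdrawals, and that this entry takes precedence over the exit rating. The documents do not describe the scale's categories, so the sponsor should check the entry against its own CGI-EI form.
- For infants with no rating at all, use the least favourable rank only in a sensitivity analysis, because some will have left for reasons unrelated to treatment.
- Report the result based on Visit 4 ratings alone as the PP analysis.

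The cost is one schedule footnote and a few sentences in the analysis section; the neurologist already seeing the infant makes the rating. The downside is small: exit ratings are made at varying times before Week 12, and the reported index may be less favourable in both arms.

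### Needing a prohibited medicine removes an infant from the whole study, which ends scheduled safety evaluation and leaves mean CAT/CLAMS, and arguably CGI-EI, with no stated Week 12 value

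*Combined protocol and SAP*

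**What the plan says.** All references are to the Combined protocol and SAP, which is a protocol summary.

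- **Study design:** "If the prohibited medicines are required for patients they will be withdrawn from the study and it will be considered as the absence of efficacy". Discontinuation criteria, item 2, lists the same event: "Necessity in the products not allowed within the study".
- **Endpoints:** there is one primary and four secondary efficacy endpoints. The primary and secondary endpoints 1 and 3 are percentages of patients. Secondary endpoint 2 is a mean: "Mean Cognitive adaptive test/Clinical linguistic and auditory milestone scale (CAT/CLAMS) by the end of the treatment course compared to baseline". Secondary endpoint 4 is the "Efficacy Index (CGI-EI) score by the end of the treatment course".
- **Safety assessment:** "Adverse events during the treatment, their severity, treatment relatedness, and outcomes".
- **Schedule of study procedures:** CAT/CLAMS is scored at Visits 1 to 4, safety is evaluated at Visits 2, 3 and 4, and CGI is scored at Visit 4 only. There is no column for an early-exit visit.
- **Prohibited concomitant therapy:** the list includes antiepileptics (item 3) and muscle relaxants (item 6). It also includes homeopathic products (item 9) and vitamins (item 10).
- **Statistical Analyses:** the safety set is every randomized infant with at least one dose. Efficacy is analysed in the FAS and the PP set. No method for missing values is given.
- **Discontinuation criteria, items 3 and 4:** item 3 speaks of the product ("Development of an adverse event requiring the product discontinuation"), while item 4 speaks of the study (the parents' "wish to terminate the study early due to lack of therapeutic efficacy or for any other reason").

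**The concern.** A failure rule answers a yes/no question. It does not produce a number for a mean or a rating. An infant who leaves early under this rule counts as a failure on the percentage endpoints, yet may be absent from mean CAT/CLAMS and CGI-EI even in the FAS. The plan itself labels these infants as failures, so any such absence is related to outcome. That is the kind of missingness a full analysis set is meant to avoid.

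On safety, symptomatic epilepsy and focal pareses are exclusion criteria (items 1.7 and 1.4). An infant who starts an antiepileptic or a muscle relaxant during the trial may therefore have a new neurological problem. The plan promises event outcomes, but the exit rule stops the visits at which they would be recorded.

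**Working it through.** **1. What the failure rule settles**

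| Efficacy endpoint | Type | Settled by the rule? |
|---|---|---|
| Primary (gain of 4 or more points, Jurba-Mastyukova) | percentage | yes |
| Secondary 1 (score of 27 or more) | percentage | on a fair reading |
| Secondary 2 (mean CAT/CLAMS) | mean | no value stated |
| Secondary 3 (quotients of 75 or more) | percentage | on a fair reading |
| Secondary 4 (CGI-EI) | score | only if read as a worst score |

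That leaves 2 of 5 endpoints without a stated value, or 1 of 5 if absence of efficacy is taken to mean the worst CGI-EI score. For CAT/CLAMS an interim score from Visit 2 or 3 may exist, but nothing says whether it is used. For CGI there is no interim score to use.

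**2. What one exit leaves undone** (from the Schedule of study procedures)

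| Exit | Weeks left | Safety evaluations lost | Post-baseline CAT/CLAMS lost | CGI lost |
|---|---|---|---|---|
| before Visit 2 | more than 8 of 12 | 3 of 3 | 3 of 3 | 1 of 1 |
| just after Visit 2 (Week 4) | (12 − 4)/12 = 67% | 2 of 3 | 2 of 3 | 1 of 1 |
| just after Visit 3 (Week 8) | (12 − 8)/12 = 33% | 1 of 3 | 1 of 3 | 1 of 1 |

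**3. How many infants**

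The plan's recruitment figure first: 72/(1 − 0.22) = 92.3 per group (stated 92), and 144/(1 − 0.22) = 184.6 in total (stated 184). The implied allowance is 184 − 144 = 40, and 40/184 = 21.7%. It covers losses at screening and during the study for any reason, and the plan words the 22% as a minimum. It therefore gives neither the number of prohibited-medicine exits nor a bound on it.

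As assumed shares only: 2%, 5% or 10% of 184 would be 3.7, 9.2 or 18.4, that is about 4, 9 or 18 infants.

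**4. Effect on mean CAT/CLAMS**

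Let m be the mean of 72 completers in an arm and x the value of one infant who exits. The mean with that infant is (72m + x)/73. Leaving the infant out shifts the arm mean by

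m − (72m + x)/73 = (m − x)/73, or 1.4% of the gap m − x.

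For k such infants with average value x, the shift is k/(72 + k) of the gap: 2/74 = 2.7% for k = 2, 5/77 = 6.5% for k = 5, and 9/81 = 11.1% for k = 9. These are shifts in one arm. Equal shifts in both arms cancel in the comparison, so what matters is an imbalance in the number of exits or in their gaps.

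**The case against.** The strongest reply is that this is a summary, and the full protocol may provide an exit visit, follow-up of open events and a rule for missing scores. That is fair for everything that is merely absent here. It does not remove the positive instruction to withdraw these infants from the study.

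Second, treating the need for another medicine as failure is a coherent composite rule in a trial that bars other treatment for 12 weeks. This stands, and the fix keeps the rule.

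Third, the safety loss is narrow. The endpoint concerns events during treatment, and every dosed infant stays in the safety set, so events up to exit still count. What may be lost within the stated endpoint is the outcome of events still open at exit. Later events would be additional information. Nor does every exit signal harm, since vitamins and homeopathic products are also on the list.

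Fourth, a Week 12 score taken after a nootropic or antiepileptic partly reflects that medicine. The same infant could then be a failure on secondary endpoint 3 and contribute an assisted score to secondary endpoint 2. This is a real tension. It is why the sensitivity analysis should assign an unfavourable value; leaving these infants out would recreate the missingness.

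A reader might also infer that infants stopped for an adverse event leave the study and lose their primary score. The documents do not establish this: item 3 of the Discontinuation criteria names the product, item 4 names the study, and both stand under one heading.

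**Conclusion.** The point holds with limited scope, as a cheap improvement worth making. Followed as written, the rule ends scheduled safety evaluation early for infants who need a prohibited medicine. It also leaves mean CAT/CLAMS without a stated value for them, and CGI-EI too unless a worst score is meant.

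Three stronger readings are not supported:

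- **The primary endpoint is compromised.** It is not, because the failure rule settles it for these infants.
- **At most 40 infants are affected.** The 40 is an all-cause planning allowance built on a minimum withdrawal rate. The number affected is unknown.
- **The comparison is biased.** No difference between arms in these exits is shown.

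The likely small effect on mean CAT/CLAMS (1.4% of the gap for one infant) assumes few such exits, reasonably balanced between arms, and 72 completers per arm. The conclusion also assumes that the full protocol does not override the exit rule in this summary.

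**What to change.** 1. Keep the absence-of-efficacy rule for the responder endpoints, and say that it covers secondary endpoints 1 and 3.
2. Replace withdrawal from the study with: stop study product and continue the scheduled visits to Week 12 unless the parents withdraw consent.
3. Record adverse events to Visit 4, report those that start after product stop separately from on-treatment events, and follow open events to resolution or stabilisation.
4. Use the observed Week 12 CAT/CLAMS and CGI-EI values in the FAS. Add a sensitivity analysis that gives these infants an unfavourable value in line with the failure rule, and fix that value in advance.
5. State whether an adverse-event stop ends product or study participation. If study exit is meant, apply the wording of step 2 there too.

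The cost is an amendment of a few sentences and one extra sensitivity analysis, with no additional patients. A small, unknown number of infants would attend already scheduled visits off product, and sites would need some contacts to close open events. Week 12 scores in these infants will partly reflect the prohibited medicine. Where parents decline further visits, Week 12 scores will still be missing.
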